4.1 Study Population

Patient subjects with a cancer diagnosis who meet the inclusion and exclusion criteria will be eligible for this study. Caregivers and Providers who meet the inclusion and exclusion criteria will be eligible for the study. Providers will include social workers, nurses, oncologists, and healthcare administrators.

4.2 Inclusion Criteria

Patients:

1. 65 years of age or older
2. Diagnosed with cancer
3. English speaking
4. Resides in non-institutional, rural settings
5. Receives care at a community-based clinic in a rural area
6. Ability to provide informed consent
7. Have an identified informal Caregiver

Caregivers:

1. Person (family member or friend) whom the patient indicates provides most of their informal care
2. Ability to provide informed consent

Providers:

1. Currently works with geriatric cancer patients
2. Currently works in a healthcare system serving geriatric cancer patients

OR

4.3 Exclusion Criteria

Patients:

1. Severe cognitive impairment (Short Portable Mental Status Questionnaire<6)
2. Receiving hospice at time of enrollment

Caregivers and Providers: None

4.4 Strategies for Recruitment and Retention

No participants will be recruited or enrolled at WCM, all recruitment and enrollment will be at Maury Regional Medical Center under their approved IRB.

A total of 40 geriatric cancer patients will be recruited across both phases once they have been identified by research and medical staff and confirmed to meet eligibility criteria. Based on prior work with cancer patient populations in rural clinic settings, we conservatively estimate that 50% of the approached patients (n=160) will be eligible to participate and consent to participate (n=80).

Caregivers of these patients will then be screened for eligibility (for Phase 1). Based on current work by the study team on cancer caregivers, we estimate that 50% of approached caregivers will be eligible and consent to participate (n=40), ensuring we hit our recruitment goal of n=10 caregivers for Phase 1. Thus, in total, 40 geriatric cancer patients and 10 informal, unpaid caregivers will participate in this study. Finally, we seek to recruit 10 oncology providers working within rural settings with the geriatric cancer patient population. In prior studies, our recruitment rates of providers have been in line with prior provider-based studies (35-50%). Thus, we conservatively estimate an accrual rate of 35%.

To recruit patients (Phase 1 and 2): Research staff will review the electronic health record to identify potentially eligible patients and will contact the treating physician to confirm initial eligibility and obtain permission to approach these patients about the study. Patients approved for contact by the treating physician will be approached in clinic or sent a letter in the mail that includes a brief description of the study and contact information of study staff. Research staff will meet these patients in the clinic, introduce themselves, and provide the patient with a study information sheet and consent form. Patients who indicate they want to participate will be consented at that time or provided a pre-paid postmarked return envelope in which to return the consent form and contacted within one week via telephone for follow-up. Patients who study staff are unable to meet during clinic appointments will be contacted by study staff over the telephone and will be provided with information on the study and administered informed consent. Once consented, participants will be enrolled in the study.

To recruit caregivers (Phase 1 only): After an eligible patient agrees to participate, we will approach his/her designated informal caregiver to participate as well. If the caregiver is present during the patient's clinic appointment, study information will be provided at that time. If the caregiver is not present, study staff will contact the caregiver over the telephone. We will provide caregivers with information about the study, address any questions or concerns they may have, obtain consent for participation, and enroll them in the study.

To recruit providers (Phase 1 only): The MPIs will send an introductory email to providers working the participating site (Maury Regional Medical Center) as well as listservs of professional societies and networks of study team members requesting that interested providers contact the study team who meet inclusion criteria (i.e., working with geriatric cancer patients in rural clinic settings). Providers who express interest will be contacted by the team and provided with information about the project and its potential risks and benefits. Providers who indicate an interest in participating will be consented.

Phase 1 participants will be compensated \$35.00 for their participation. Phase 2 participants will be compensated \$25.00 for completing pre-intervention assessments and \$25.00 for completing post-intervention assessments.

5. Registration Procedures

5.1 Subject Registration (WCM only)

Subjects will not be registered within the WRG-CT as per the standard operating procedure for Subject Registration because subject enrollment will be at and under the IRB of Maury Regional Medical Center.

5.2 Subject Registration (Sub-sites)

Not applicable

6. Study Procedures

6.1 Schedule of Assessments

Table 1. Schedule of trial events

	Phase 1		Phase 2			All Phases	
	Pre-Study	Visit 1	Pre-Study	Wk 1	Wk 2	Wk 3	
Informed consent	X		X				
Review of Intervention Draft		X					
Qualitative Interview		X					
Demographics		X		X			
Clinical Variables							X
Intervention					X		
Feasibility				X		X	
Feasibility				X		X	
Treatment Fidelity				X		X	
Pain Self-Management				X		X	
Pain Misconceptions				X		X	
Self-efficacy for communicating w/physicians about pain severity				X		X	
Pain-Related Impairment				X		X	
Pain Severity				X		X	
Intervention					X		

7.0 Data Reporting / Regulatory Considerations

7.1 Data Collection

Data will be collected and stored at Maury, on their secured servers on password protected computers under their IRB protection. Only de-identified data will be shared with Planetree and WCM, and will not include PHI or MRNs. etc. All data will be stored on secure servers on password protected computers. Only IRB approved study staff will have access to these data.

7.1.1 REDCap

Not Applicable

7.2 Regulatory Considerations

7.2.1 Institutional Review Board/Ethics Committee Approval

As required by local regulations, the Investigator will ensure all legal aspects are covered, and approval of the appropriate regulatory bodies obtained, before study initiation.

Before initiation of the study at each study center, the protocol, the ICF, other written material given to the patients, and any other relevant study documentation will be submitted to the appropriate Ethics Committee. Written approval of the study and all relevant study information must be obtained before the study center can be initiated or the IP is released to the Investigator. Any necessary extensions or renewals of IEC/IRB approval must be obtained for changes to the study, such as amendments to the protocol, the ICF, or other study documentation. The written approval of the IEC/IRB together with the approved ICF must be filed in the study files.

The Investigator will report promptly to the IEC/IRB any new information that may adversely affect the safety of the subjects or the conduct of the study. The Investigator will submit written summaries of the study status to the IEC/IRB as required. On completion of the study, the IEC/IRB will be notified that the study has ended.

Neither the Investigator nor BMS will modify or alter this protocol without the agreement of the other. All agreed protocol amendments will be clearly recorded on a protocol amendment form and will be signed and dated by the original protocol approving signatories. All protocol amendments will be submitted to the relevant institutional IEC/IRB for approval before implementation, as required by local regulations. The only exception will be when the amendment is necessary to eliminate an immediate hazard to the trial participants. In this case, the necessary action will be taken first, with the relevant protocol amendment following shortly thereafter.

Once protocol amendments or consent form modifications are implemented at the lead site, Weill Cornell Medicine, updated documents will be provided to participating sites. Weill Cornell Medicine must approve all consent form changes prior to local IRB submission.

Relevant study documentation will be submitted to the regulatory authorities of the participating countries, according to local/national requirements, for review and approval before the beginning of the study. On completion of the study, the regulatory authorities will be notified that the study has ended.

7.2.2 Ethical Conduct of the Study

The Investigators and all parties involved should conduct this study in adherence to the ethical principles based on the Declaration of Helsinki, GCP, ICH guidelines and the applicable national and local laws and regulatory requirements.

This study will be conducted under a protocol reviewed and approved by the applicable ethics committees and investigations will be undertaken by scientifically and medically qualified persons, where the benefits of the study are in proportion to the risks.

7.2.3 Informed Consent

The investigator or qualified designee must obtain documented consent according to ICH-GCP and local regulations, as applicable, from each potential subject or each subject's legally authorized representative prior to participating in the research study. Subjects who agree to participate will sign the approved informed consent form and will be provided a copy of the signed document.

The initial ICF, any subsequent revised written ICF and any written information provided to the subject must be approved by IRB prior to use. The ICF will adhere to IRB/IEC requirements, applicable laws and regulations.

Informed Consent will occur under the IRB of Maury Regional Medical Center.

7.2.4 Compliance with Trial Registration and Results Posting Requirements

Under the terms of the Food and Drug Administration Modernization Act (FDAMA) and the Food and Drug Administration Amendments Act (FDAAA), the Sponsor-Investigator of the trial is solely responsible for determining whether the trial and its results are subject to the requirements for submission to <http://www.clinicaltrials.gov>. Information posted will allow subjects to identify potentially appropriate trials for their disease conditions and pursue participation by calling a central contact number for further information on appropriate trial locations and trial site contact information.

7.2.5 Record Retention

Essential documents are those documents that individually and collectively permit evaluation of the study and quality of the data produced. After completion of the study, all documents and data relating to the study will be kept in an orderly manner by the Investigator in a secure study file. Essential documents should be retained for 2 years after the final marketing approval in an ICH region or for at least 2 years since the discontinuation of clinical development of the IP. In addition, all subject medical records and other source documentation will be kept for the maximum time permitted by the hospital, institution, or medical practice.

8. Statistical Considerations

We will employ thematic analysis using an iterative process for all qualitative analyses.¹⁹⁻²³

Phase 1. Data coding and analysis will be informed by a responsive interviewing model in which data units are combined based on the theme they represent.²⁴ Trained raters will independently review the transcripts and identify passages that include suggestions for modifications to the intervention. Raters will categorize and discuss themes, and make revisions until consensus is reached. Identified themes will inform modifications to the intervention. **Phase 2a.** Feasibility and acceptability will be examined by conducting frequency and descriptive statistics (i.e., mean, median, standard deviation, range) for enrollment rates, number of sessions completed, number of weeks required to complete the intervention, and Likert-scale items assessing satisfaction with the intervention and perceived helpfulness. **Phase 2b.** Aim 3 will be addressed using a pre-post design. To determine the degree to which the Ca-HELP intervention is likely to improve patient outcomes, a post-versus-pre- difference will be sought to estimate the change in patients' outcomes (e.g, pain self-management). **Missing data.** To reduce missing data, study staff will conduct interviews rather than relying on written self-reports. All missing data will be assessed for missingness (e.g., random or non-random) and appropriate imputation methods will be used.

9. Adverse Event Reporting Requirements

Not Applicable – No subjects will be enrolled at WCM.

10. Unanticipated Problems Involving Risks to Subjects or Others

Not Applicable – No subjects will be enrolled at WCM

References

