3.1 Overall Design

No participants will be recruited or enrolled at WCM, all recruitment and enrollment will be at Maury Regional Medical Center under their approved IRB.

Phase 1: Patients, caregivers, and providers will first provide informed consent. Next, we will provide participants with drafts of intervention workbook content to review. We will then conduct semi-structured qualitative interviews in-person or over the telephone with 10 geriatric cancer patients, 10 informal caregivers, and 10 providers in which they will answer questions about how they might use the intervention workbooks, the clarity and readability of the workbooks, and the feasibility and utility of the structure of the intervention (e.g., number of sessions, session frequency). Additionally, participants will be probed about necessary modifications in order to make the Ca-HELP intervention workbook content appropriate for the geriatric cancer patient population. As outlined in the research strategy, this feedback will be obtained through semi-structured interviews, through a steering committee, and through implement the un-adapted program to obtain recommendations for necessary change. Patients, caregivers and providers will be compensated with \$35.00 for their participation.

Phase 2: Patients and caregivers will first provide informed consent and then will be administered pre-intervention study surveys over the telephone. They will then participate in the intervention in person or over the telephone, depending on the recommended results from completion of Aim 1. Following intervention completion, post-intervention study surveys will be administered over the telephone. Study staff will extract data (e.g., disease stage, etc.) from the electronic health record. Patients will be compensated with \$25.00 for completing pre-intervention assessments and \$25.00 for completing post-intervention assessments.

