The following steps will be taken to minimize participant burden. First, significant effort will be made to coordinate in-person study contacts (e.g., to provide information on the study and administer informed consent) with existing appointments to minimize the number of trips to Maury Region Medical Center required of participants. Second, with the participant's permission, these study visits (for Aim 1) can be conducted during scheduled chemotherapy infusions (if applicable, as some cancer patients will not be receiving chemotherapy). Chemotherapy infusion appointments are often long (multiple hours) and patients are unable to leave the clinic during the appointment. In a previous R01 study (Co-I: [name]) of psychosocial distress in adults with advanced cancer, patients often elected to conduct research meetings during infusion appointments to provide activity during the appointment and reduce the overall time spent at the hospital. Prior to conducting visits during infusion appointments, participants will be reminded that infusion clinics are often not private and their permission to conduct the visit during infusion will be obtained. Participants will also be informed that they can discontinue at any time if they become uncomfortable due to the setting. If participants are not comfortable conducting visits during infusion appointments, separate appointments will be scheduled in person or over the telephone. Similar measures will be taken to reduce the burden on caregivers participating in this study and all efforts will be made to coordinate study visits during times when they are already at the hospital with the patient. Third, participants will be given the option to complete the semi-structured interviews for Aim 1 over the telephone and administration of all study measures for Phase 2 will occur in person or over the telephone, depending on patient preference. This method will eliminate the need for participants to travel to the clinic to complete study measures. Finally, intervention sessions may be conducted over the telephone with patients, depending on the results of Phase 1 and preferences of the patient

population. Telephone delivery may allow patients to participate in the intervention without traveling to the clinic multiple times for intervention sessions.

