3.2 Interviews, Focus Groups, Surveys, and/or Observations

No participants will be recruited or enrolled at WCM, all recruitment and enrollment will be at Maury Regional Medical Center under their approved IRB.

A. Administration

- *Timing and Frequency*

Phase 1: 1 interview

Phase 2: Pre-interview/Baseline assessment, intervention call, and post assessment each approximately 1 week apart for a total of 3 weeks.

- *Location*

All phases: Telephone interview at a convenient location to the participants. Cancer patients may opt to have their interview(s) during infusion at Maury Regional Medical Center

- *Procedures For Audio And Visual Recording*

Not Applicable

- *Person Identifiers*

Clinical variables will be collected from medical records and will include the following: cancer diagnosis and stage, treatment received, co-morbid conditions, and Karnofsky performance status.

B. Study Instruments

All Phases: Demographics will be measured via self-report assessing: age, gender, race, ethnicity, marital and parental status, employment status, education, income, religious affiliation, and insurance coverage. **Clinical variables** will be assessed using records from medical charts and will include the following: cancer diagnosis and stage, treatment received, co-morbid conditions, and Karnofsky performance status.¹⁵

Phase 2a: Feasibility will be assessed by accrual rates and rate of intervention completion.

Acceptability will be assessed with Likert scale and a semi-structured interview assessing perceived helpfulness, satisfaction, usability, readability, and intervention impact. **Treatment fidelity** will be assessed with a checklist that captures whether session content was delivered and appropriate techniques were utilized.

Phase 2b: Pain self-management will be measured using two items from the pain management subscale of the Chronic Pain Self-Efficacy scale.¹¹ **Pain misconceptions** will be assessed using the 11 items based on the SBQ.¹⁶ **Self-efficacy** for communicating with physicians about pain severity will be assessed using the 5-item Perceived Efficacy in Patient-Physician Interactions scale¹⁷ as modified to refer to communication with oncologists.¹¹ **Pain-related impairment** will be measured using the 6-item Medical Outcomes Study (MOS) Pain Impairment Scale.¹⁸ **Pain severity** will be assessed as the mean of the average and worst pain over the past two weeks on a 0 to 10 scale (0 = no pain and 10 = worst pain imaginable).¹¹

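### Does the Not Applicable entry for recording in Section 3.2 leave the Phase 1 transcript coding in Section 8 without a source?

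*Combined protocol and SAP*

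**What the plan says.** Section 3.1 plans to "conduct semi-structured qualitative interviews in-person or over the telephone with 10 geriatric cancer patients, 10 informal caregivers, and 10 providers", and Section 3.2 A gives each Phase 1 participant one interview. Section 8 states the general approach, "We will employ thematic analysis using an iterative process for all qualitative analyses", and then the Phase 1 step: "Trained raters will independently review the transcripts and identify passages that include suggestions for modifications to the intervention". The raters go on to categorise and discuss themes until they agree, and the themes inform changes to the intervention.

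Section 3.2 A contains the entry "Procedures For Audio And Visual Recording", answered Not Applicable with no reason and no limit to a site or phase. The same section opens by saying that nobody is recruited or enrolled at WCM and that enrolment takes place at Maury Regional Medical Center under that centre's IRB approval. On location it adds: "Cancer patients may opt to have their interview(s) during infusion at Maury Regional Medical Center".

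Section 7.1 (Data Collection) covers storage at the enrolling site and transfer of de-identified data to the two analysing institutions. It does not mention recordings, notes or transcription.

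**The concern.** Independent coding by several raters needs a fixed text that all of them can read. Section 8 names that text, while the one entry in the protocol that deals with capturing interviews appears to say nothing is recorded. Read together, the Phase 1 coding seems to lack a defined source.

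The source limits what the raters can find. If the interviewer does not write down a suggestion, no amount of double coding brings it back, and with one interview per participant there is no second chance to collect it. The coded themes feed the version of the intervention used in Phase 2, so a thin source could weaken the adaptation without anyone noticing.

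The infusion clinic raises a further question. Section 3.1 says "participants will be reminded that infusion clinics are often not private", so one may ask whether patient interviews held there could be recorded at all.

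**Working it through.** No power or sample-size formula applies. The check is a reading of the relevant sections side by side, plus one count.

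**Count.** Section 3.1 gives 10 patients, 10 caregivers and 10 providers; Section 3.2 A gives one interview each. (10 + 10 + 10) × 1 = 30 interviews. Section 8 does not state this total.

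**Is a method of capture stated anywhere?** Transcripts are mentioned only in Section 8. Section 3.1, the schedule in Section 6.1 and Section 7.1 say nothing about audio, notes or transcription. The omission is real in the supplied text. Consent pages were removed before review and may deal with recording, so actual practice cannot be judged from what remains.

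**Do Sections 3.2 and 8 contradict each other?** Only if a transcript must come from a recording. Near-verbatim notes taken during a telephone or in-person interview also give raters a text to review independently. The protocol does not say this is intended, but nothing in it rules it out. What is established is an unstated method, not an impossible analysis.

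**Could the entry refer to WCM only?**
- Against: Sections 9 and 10 give their reason in words, "No subjects will be enrolled at WCM", and the recording entry gives none. The timing and location entries beside it describe interviews with participants at the enrolling site.
- For: Section 3.2 opens with the statement that WCM enrols nobody. Bare Not Applicable answers also occur elsewhere. Section 5.2, on registration at sub-sites, has one although another centre enrols every participant, and Section 7.1.1, on REDCap, has one directly after text placing the data at that centre. The lack of a stated reason therefore says little about scope.

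The WCM-only reading is unproven but plausible.

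**What depends on it?** Section 1.1.2 states hypotheses for Phase 2 only. Phase 1 has no endpoint, estimate or decision threshold. Section 3.1 says "this feedback will be obtained through semi-structured interviews, through a steering committee, and through implement the un-adapted program", and Section 1.1.1 adds theory and mixed methods analysis. Interviews are one input among several.

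**Does the infusion setting change the picture?** Up to 10 of the 30 interviews (10/30 = 33%) are patient interviews, some of which might be held during infusion. That share describes privacy, not whether a transcript exists. Section 3.1 already handles privacy with a reminder, permission beforehand, the right to stop, and a separate visit or telephone call instead.

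**The case for a change.** The strongest case for a change is that reconciling the sections is cheap and has to happen early. Each participant is interviewed once, so capture must be settled before the first interview. The enrolling site collects the data and other institutions analyse them, so recordings or verbatim text would need de-identifying before transfer, and the protocol sets out no such step for interview material. Even on the WCM-only reading, the document never says how transcripts are made. If the consent form does allow recording, a bare Not Applicable in Section 3.2 is misleading.

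Much of this stands. The omission is real, the two sections read poorly together, and a sentence on capture would make the document clearer. It does not show that following the plan leads to a wrong result. Staff told to give raters transcripts must decide how to make them, and Section 7.1 already limits what may leave the site. Either remedy, describing recording or calling the source notes, would write down a choice that has to be made anyway; the second alters wording only. The independent review that protects the coding is already in Section 8.

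The Phase 2a acceptability interview, for which Section 8 names no source, is a separate question and adds nothing to the size of this one.

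**Conclusion.** The point is accurate as an observation: for 30 Phase 1 interviews, the protocol calls for transcripts, answers Not Applicable on recording, and never states how the text is produced. It does not call for a change to the plan. The sections are compatible if notes serve as the source, or if the recording entry was completed for WCM alone. The documents do not settle which holds. Phase 1 is formative, with no hypothesis or threshold that the choice of source could shift, and no numerical consequence can be attached to it.

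This conclusion assumes that the enrolling site settles capture under its own IRB before interviewing begins, and that raters receive a text complete enough to code. Both are ordinary practice for this kind of work, and nothing in the documents suggests otherwise. The mismatch is best treated as a form entry and an operational detail for the study team to make clear in its interview procedure.
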